# 2. LIST OF ABBREVIATIONS

Abbreviation	Definition
3CL	3C-like protein
COVID-19	Coronavirus disease 2019
EDC	Electronic data capture
FDA	Food and drug administration (United States)
ICH	International conference on harmonisation
IEC	Independent ethics committee
IRB	Institutional review board
N/A	Not applicable
SAP	Statistical analysis plan
SARS-CoV-2	Severe acute respiratory syndrome coronavirus 2

# 3. RESPONSIBLE PARTIES

The Japan Good Post-marketing Study Practice officer

# 4. AMENDMENTS AND UPDATES

Amendment number	Date	Protocol Section(s) Changed	Summary of Amendment(s)	Reason
Amended 2	31 January 2023	5. MILESTONES	Addition of items and update of contents	Administrative changes
		6. RATIONALE AND BACKGROUND	Update of ministerial ordinances, notifications, etc.	Due to the partial revision of the ministerial ordinance
		8.9. Limitations of the research methods	Terminology changes, etc.	Administrative changes
		9.4. Ethical conduct of the study		
		10. MANAGEMENT AND REPORTING OF ADVERSE EVENTS/ADVERS E REACTIONS	Changes in Japanese translation, etc., and maintenance of descriptions	Due to changes in association with a revision of the in-house form
		12. NAME, AND ADDRESS OF CONTRACTOR AS WELL AS SCOPE OF WORK CONTRACTED	Maintaining address information	Administrative changes
		16.2. Contact information for inquiries about the EDC system (In the case of study using EDC)	Changes in contact information for inquiries	Due to changes in the information concerning contact information
Amended 1	28 June 2022	7.1. Safety specifications	Added anaphylaxis to important identified risks	Due to the revision of safety specification in the Risk Management Plan
		8.7. Data analysis	Definition of analysis set     Change before:  R CONFIDENTIAL	The effectiveness analysis set was not a subset of safety populations,

			· Effectiveness Analysis Set 1: A population of patients in the SAS excluding patients for whom effectiveness evaluation is not reported at all or whose disease is not subject to the study After change: · Effectiveness Analysis Set 1: A population of patients in which effectiveness can be evaluated among patients in which this drug was administered	but effectiveness evaluable among all patients with administration
		10. MANAGEMENT AND REPORTING OF ADVERSE EVENTS/ADVERS E REACTIONS	Changes in Japanese translation, etc., and maintenance of descriptions	Due to changes in association with a revision of the in-house form
		12. ORGANIZATION AL SYSTEM FOR STUDY IMPLEMENTATIO N	Item Removal (Subsequent section numbers moved up)	Administrative changes associated with the Notification "Formulation and Publication of Risk Management Plans" dated 18 March 2022
FINAL	08 February 2022	N/A	N/A	N/A

# 5. MILESTONES

Milestone	Planned date
Start of investigation period	February 2022
Start of data collection (registration date of the first subject)	31 March 2022
End of investigation period	April 2024
End of data collection (release date of the database)	November 2024
Interim report	28 September 2022
Final study report	October 2025

#### 6. RATIONALE AND BACKGROUND

PAXLOVID® PACK (generic name: nirmatrelvir tablets and ritonavir tablets) (hereinafter, this drug) is a combination of nirmatrelvir, an inhibitor of SARS-CoV-2 3CL protease, and ritonavir, a potent inhibitor of CYP3A4. The combination of the 2 drugs will maintain exposure to nirmatrelvir to inhibit viral replication throughout the treatment period. The marketing authorization of this drug was obtained in February 2022 in Japan for the indication of "Disease caused by SARS-CoV-2 infection (COVID-19)."

The objective of the "PAXLOVID® PACK General Investigation" (hereinafter, this study) is to assess the safety and effectiveness of this drug under post-marketing actual status of use.

This study shall be conducted in strict compliance with the "MHLW Ordinance on the Standard for Post-Marketing Studies and Clinical Trials of Medical Products" (MHLW Ordinance No. 171, dated December 20, 2004), the "Enforcement of the MHLW Ordinance on the Standard for Post-marketing Studies and Clinical Trials of Medical Products" (PFSB Notification No. 1220008, dated December 20, 2004), "MHLW Ordinance on the Standard for Post-marketing Safety Control of Medical Products, Quasi-medical Products, Cosmetics, Medical Devices and Regenerative Medical Products" (MHLW Ordinance No. 135, dated September 22, 2004), the "Enforcement of the MHLW Ordinance on the Standard for Postmarketing Safety Control of Medical Products, Quasi-medical Products, Cosmetics, and Medical Devices, Regenerative Medical Products" (PFSB Notification No. 0812-4, dated August 12, 2014), "MHLW Ordinance to Partially Amend the MHLW Ordinance on the Standard for Post-marketing Studies and Clinical Trials of Medical Products" (MHLW Ordinance No. 116, dated October 26, 2017), and "Announcement of the MHLW Ordinance to Partially Amend the MHLW Ordinance on the Standard for Post-marketing Studies and Clinical Trials of Medical Products (Regarding the MHLW Ordinance on the Standard for Post-Marketing Studies and Clinical Trials of Medical Products)" (PSEHB Notification No. 1026-1, dated October 26, 2017).

#### 7. RESEARCH QUESTION AND OBJECTIVES

The objective of this study is to assess the safety and effectiveness of this drug under post-marketing actual status of use in patients receiving this drug.

# 7.1. Safety specifications

Important Identified Risks: Toxic epidermal necrolysis/oculomucocutaneous syndrome, hepatic function disorder and anaphylaxis

Important Potential Risks: Hyperglycemia/diabetes mellitus and bleeding tendencies

#### 8. RESEARCH METHODS

# 8.1. Study design

This study is an open-label, multi-center, one arm prospective observational cohort study of patients receiving this drug. The investigators complete the CRF based on the information extracted from the medical record created in daily medical practice.

### 8.2. Setting

Patients who satisfy all of the registration criteria are subject to this study.

# 8.2.1. Registration criteria

Patients must meet all of the following inclusion criteria to be eligible for inclusion in this study:

Patients who receive this drug for the first time.

In principle, data will be collected prospectively. However, in order to collect data at an early stage after approval as much as possible, patients who started to receive this drug before conclusion of the contract may be enrolled in this study.

Refer to the latest package insert of this drug for "indications" and "dosage and administration" when this drug is administered.

[Indications]

Disease caused by SARS-CoV-2 infection (COVID-19)

[Dosage and administration]

The usual dosage in adults and pediatric patients ( $\geq$ 12 years of age weighting  $\geq$ 40 kg) is 300 mg of nirmatrelvir and 100 mg of ritonavir all taken together orally twice daily for 5 days.

#### 8.2.2. Exclusion criteria

There are no exclusion criteria for this study.

#### 8.2.3. Study sites

Plan to conduct this study at 400 sites including the Department of Infectious Diseases, Department of Internal Medicine, etc.

# 8.2.3.1. Site requirements

Sites where patients can be followed up at the time of the site visit or by telephone, home visit, etc. after administration of this drug.

# 8.2.4. Planned study period

The planned period covered by this study is as follows.

Investigation period: February 2022 to April 2024 (from the start of the registration period to the completion of the observation period of the last patient.)

Registration period: February 2022 to February 2024

The registration is terminated if the target number of the patients has been collected, even before the end of the registration period.

# 8.2.5. Study procedures

# **8.2.5.1.** Study method

Continuous registration system: This study will be conducted with continuous registration system that patients who meet the registration criteria of this study will be registered sequentially until data are collected on a target number of patients for each investigation sites.

#### 8.2.5.2. Request for cooperation in the study and contract

- 1. The site staff will explain the outline of this study to the physicians who are registered at PAXLOVID® PACK Registration Center and plan to use this drug.
- 2. If the site is selected as a study site, the site staff will conclude a contract for this study with the site.

#### 8.2.6. Observation period

From the start date of administration to 28 days after the completion of administration (The day after the completion of administration is Day 1.)

#### 8.3. Variables

This study will be conducted according to the following schedule of observation.

Table 1. Variables and schedule of observation

Variable	Registration form	CRF Until 28 days after the completion of administration of this drug
ID number	•	*
Gender	•	*
Birth year and month/age	•	*
Eligibility	•	
Start date of treatment with this drug	•	*
Height/body weight		•
History of smoking		•
Presence/absence of symptoms of the target disease, severity, and date of onset		•
Presence/absence of liver functional impairment and renal functional impairment, severity		•
Disease history		•
Prior medications for infections caused by SARS-CoV-2		•
History of SARS-CoV-2 vaccination		•
Presence/absence of pregnancy (only for women)		•
Presence/absence of findings of pneumonia attributable to infections caused by SARS-CoV-2 at the start of administration		•
Hospitalization status		•
Targeted drug use record		•
Concomitant therapy (Drug therapy/ Non-drug therapy)		•
Tests (virus/vital signs)		•
End-of-study/Discontinuation record (reason)		•
Effectiveness evaluation		•
Adverse events		•
Informed consent for publication of results		•

\* Some elements in the Registration Form are automatically reflected in the CRF. The investigators should check and update the CRF as needed.

# 8.3.1. Patient characteristics

- 1. Enter the information at the start of administration of this drug into the registration form
  - ID number
  - Gender

- Birth year and month/age (if birth year and month cannot be disclosed, age at the start of administration of this drug)
- Start date of treatment with this drug
- Eligibility
- 2. The following will be recorded in CRF at the start of administration of this drug:

(ID number, gender, and birth year and month/age in the Registration Form are automatically reflected in the CRF. The investigators should check and update the CRF as needed.

- ID number
- Gender
- Birth year and month/age
- Height (cm)
- Weight (kg)
- History of smoking
- Presence/absence of symptoms of the target disease (disease for which this drug is used), severity, and date of onset

The presence/absence of symptoms will be judged based on the clinical symptoms related to infections caused by SARS-CoV-2, including but not limited to the symptoms shown below.

Cough, shortness of breath or dyspnea, feeling hot, chills or shivering, fatigue (decreased energy or feeling tired), muscle pain or body pain, diarrhea (loose or watery stools), nausea (queasy), vomiting, headache, sore throat, stuffy or runny nose, dysosmia, dysgeusia, and findings of pneumonia

Severity should follow the severity classification in the "Clinical Practice Guidance for New Coronavirus Infection COVID-19" (see Table 2).

**Table 2.** Severity classification

Severity	Oxygen saturation	Clinical status
Mild	SpO 2 ≥96%	No respiratory symptoms, or cough alone with no dyspnea
		No finding of pneumonia in either case
Moderate I	93% <spo2<96%</spo	Dyspnea, pneumonia findings
No respiratory failure	9370\SpO 2 \9070	Dyspica, pileumonia midnigs
Moderate II		
Respiratory failure	SpO 2 ≤93%	Oxygen required
present	_	
Severe		Admitted to ICU or requiring mechanical
Severe		ventilation

#### Note

- It is desirable to measure SpO2 and objectively judge the state of oxygenation.
- In order to confirm the presence/absence of pneumonia, it is desirable to take measures against nosocomial infection and take chest CT scans to the extent possible.
- If there is a difference in severity between oxygen saturation and the clinical status, the higher severity should be assigned.

Excerpted from the Clinical Practice Guidance for New Coronavirus Infection COVID-19 Version 6.2 (27 January 2022)

- Presence/absence of liver impairment/renal impairment\*, severity
  - \*Liver impairment/renal impairment are not transient laboratory abnormalities but represent events that require clinical consideration and follow-up.

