# 8.3.6.2. Non-drug therapy

Regarding non-drug therapy for infections caused by SARS-CoV-2 performed during the observation period, the following information should be recorded. If an adverse event is observed, non-drug therapy used for the treatment of the adverse event should also be recorded.

- 1. The name of the therapy (oxygen administration, etc.)
- 2. Period of the therapy
- 3. Reason for the therapy (infections caused by SARS-CoV-2, adverse events, other)

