### **8.3.7.2.** Vital signs

Results of tests performed before administration (including the start date of administration) and during observation period should be recorded.

- 1. Date of tests
- 2. Items of tests
  - Body temperature and percutaneous arterial oxygen saturation (SpO2)

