# 8.3.9. Effectiveness evaluation (severity)

The presence/absence of worsening of the severity of infections caused by SARS-CoV-2 after administration of this drug during the observation period (until Day 28 after the completion of administration [including Day 28]), highest severity, and presence/absence and severity of symptoms on the end date of the observation period (date of medical examination on or after Day 28 after the completion of administration) should be entered. For cases discontinuing observation in less than 28 days after the completion of administration, the highest severity by that point and the severity as of the date of discontinuation of the observation period should be recorded (see Table 2 for severity).

- 1. Worsening of severity after administration
  - Presence/absence of worsening of symptoms
  - Date of highest severity
  - Highest severity
- 2. Severity on the end date of the observation period
  - Date of evaluation
  - Presence/absence of symptoms of infections caused by SARS-CoV-2
  - Severity

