7. HANDLING OF MISSING DATA

If the seriousness, causal relationship, treatment, and outcome of an adverse event are missing, the data will be handled as "unknown" for tabulation.

If there are no measured values within the acceptable window for each time point of evaluation of efficacy endpoints (Appendix 2), the values will be handled as missing and will not be imputed. Definitions of acceptable windows for other endpoints are provided in Appendix 2.

If the date of admission is missing or partial, the last complete date among the following will be used as the imputed date.

- Start date of this drug
- The first day of the month of the same month as the date of admission (if the day of admission is missing and the month and year are available)
- The first day of the year of the same year as the date of admission (if the month and day of admission are missing and the year is available)

If the date of death and the date of last observation are missing or partial, the latest complete date among the following will be used as the imputed date.

- Start date/end date of this drug
- Start date/end date of concomitant drug therapy
- Start date/end date of concomitant non-drug therapy
- Viral test
- Date of measurement of body temperature/SpO₂
- Date of admission/date of discharge
- Date of efficacy evaluation (date of the highest severity/date of evaluation at the end of the observation period)
- Date of onset of adverse event, resolution/recovery of adverse event, date of death
- The first day of the month of the same month as the date of last observation (if the day of last observation is missing and the month and year are available)
- The first day of the year of the same year as the date of last observation (if the month and day of last observation are missing and the year is available)

The policy for handling uncleaned data is described below.

- Items of missing data: Values will be handled as missing (category of categorical variables is "not recorded") in both tabulation and listing.
- Items of inconsistent data: Inconsistent data will be handled as missing in both tabulation and listing. However, a list of data handling will be prepared separately.
- No signature: The descriptions in the CRF without the signature of the contract physician (including the case of only the signature of a physician other than the contract physician) will be handled as missing in both tabulation and listing.

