10.2. Appendix 2: Data Extraction Details

 Table 2.
 Definitions of Acceptable Windows for Timing

Timing	Endpoint	Definition [acceptable window]
At the start of treatment	Efficacy endpoints, viral load, body temperature, percutaneous arterial oxygen saturation	From 30 days prior to the date of first dose in this study (start date of treatment) to the start date of treatment
During the observation period	Safety endpoints, efficacy endpoints, viral load, body temperature, percutaneous arterial oxygen saturation, concomitant drug therapy, and non-drug therapy	Start date of treatment to Day 28 after the end of treatment
End date of the observation	Efficacy endpoints	Primary definition: Up to Day 28 after the end of treatment
period		Secondary definition 1: Up to 42 days after the end of treatment
		Secondary definition 2: Entire period

10.3. Appendix 3: Data Entries Related to Efficacy Endpoints and Their Handling, and Assessment of Endpoints

Table 3. Worsening of Severity and Highest Severity of Infection Caused by SARS-CoV-2

Symptoms	Severity at			Worsening of	of severity: H	ighest sev	erity			
at the start of	the start of treatment	Worsening	Vorsening of severity during the observation period							
treatment	with this	Absent		Present						
with this	drug	Highest seve	erity	ity						
drug		NA	Mild	Moderate I	Moderate II	Severe	Unknown	NA		
Absent	NA	Absent: NA	Present: Mild	Present: Moderate I	Present: Moderate II	Present: Severe	Present: Unknown	Unknown: NA		
Present	Mild		Case 1				Case 2			
	Moderate I									
	Moderate II									
	Severe	Severe at the start: NA	Case 3							
	Unknown	Absent: NA	Case 4							
Unknown	NA	Case 5								

NA: not applicable

Discrepancies between evaluations at the start of treatment with this drug and during the observation period are subject to re-investigation, but the reasons for being subject to re-investigation and handling of cases where there is no change as a result of re-investigation are shown below.

- Case 1: Assessed as "Unknown: NA" because the highest severity is lower than the severity at the start of treatment with this drug.

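### The SAP severity endpoints rest on physician-entered fields alone; no stated rule checks them against recorded COVID-19 oxygen, ventilation or SpO2, so moderate II or severe outcomes can be undercounted

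*Protocol*

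**What the plan says.** **How severity is graded.** Protocol 8.3.1, Table 2, places "Oxygen required" and SpO2 of 93% or less at Moderate II. The Severe row begins "Admitted to ICU or requiring mechanical" and continues with ventilation. The Note adds: "If there is a difference in severity between oxygen saturation and the clinical status, the higher severity should be assigned". Protocol 8.3.9 refers the investigator back to Table 2 for the highest severity and the severity at the end of observation. The worsening item itself is worded "Presence/absence of worsening of symptoms".

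**What is recorded separately.** Protocol 8.3.3 collects pneumonia findings at the start. Section 8.3.6.2 collects non-drug therapy ("The name of the therapy (oxygen administration, etc".) with its period and reason, COVID-19 being one of the reasons. Section 8.3.7.2 collects dated "Body temperature and percutaneous arterial oxygen saturation".

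**What the SAP uses.** Section 6.2 and Tables 3 and 5 of Section 10.3 build worsening, highest severity, the moderate II or severe event, and improvement from symptom status, start severity, the worsening entry, highest severity with its date, and end severity. The note under Table 3 says: "Discrepancies between evaluations at the start of treatment with this drug and during the observation period are subject to re-investigation". For data that remain uncleaned, SAP 7 says: "Inconsistent data will be handled as missing in both tabulation and listing". Its next sentence announces a separate list of data handling, which is not among the documents.

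**Where oxygen does appear.** It is in the baseline and concomitant-therapy tables (8.2.2.1) and in a patient listing (9). Non-drug therapy for COVID-19 also enters the sensitivity definition of hospitalization (6.2).

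**The concern.** The items that define the upper grades in Table 2 are collected, dated and, for therapies, labelled with a reason. The endpoints that report those grades never consult them. If the entered grade is right, nothing is lost. If it is too low, unknown or missing, a patient given oxygen for COVID-19 after the start of treatment does not count as a moderate II or severe outcome, although the database holds the information to show it.

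The loss runs in one direction for that event. The study has one arm, is open-label and draws on routine records, so no comparison group would share and offset the loss, and an undercount makes the drug look better.

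**Working it through.** **Plan figures.** No number in the plan bears on this point. The sample-size figures do reproduce: 1 − 0.999^3000 = 0.950, and P(X ≥ 214) for a binomial with n = 3000 and p = 0.078 is 0.920. Only the 3,000 is used below, as a round denominator.

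**Step 1: apply the SAP rules to a patient with recorded COVID-19 oxygen.** Table 2 would grade this patient at least Moderate II. The seven possible CRF entry patterns score as follows under SAP 6.2 and Table 3.

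| Worsening entry | Highest severity entry | Initial mild | Initial moderate I |
|---|---|---|---|
| Absent | none | Not worsened, no event | Not worsened, no event |
| Unknown | none | Unknown, no event | Unknown, no event |
| Present | Unknown | Worsened, highest unknown, no event | Worsened, moderate II or severe, **event** |
| Present | Mild | No event | Unknown (Case 1), no event |
| Present | Moderate I | No event | No event |
| Present | Moderate II | **Event** | **Event** |
| Present | Severe | **Event** | **Event** |

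No moderate II or severe event results in 5 of 7 patterns for initial mild and 4 of 7 for initial moderate I. These are counts of patterns, not of patients. Where the highest grade equals the start grade, the layout of Table 3 does not show clearly whether Case 1 applies; neither reading gives an event.

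**Step 2: compare the two cells for an unknown highest grade.** The SAP infers a grade when the start was moderate I or moderate II, but has no rule when the start was mild. Recorded oxygen would settle that case under Table 2, and it is not consulted.

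**Step 3: missing efficacy page.** In SAP Table 1, cases 4 and 7 are included in Efficacy Analysis Set 1 with severity unknown, whatever the therapy page shows.

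**Step 4: direction.** With k events, losing one can only reduce the count. If the denominator is patients with worsening (8.2.4.1) and has n members, the proportion falls too: (k − 1)/n < k/n if the patient stays in the denominator, and (k − 1)/(n − 1) < k/n if the patient drops out of it and k < n.

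**Step 5: illustration of size.** The documents give no event rate and no misgrading rate, so both are assumed. With N = 3,000, a true proportion p and a missed fraction m, observed events = N × p × (1 − m), rounded to whole patients.

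| Assumed true proportion | True events | 10% missed | 50% missed |
|---|---|---|---|
| 0.5% | 15 | 14 (0.47%) | 8 (0.27%) |
| 1.0% | 30 | 27 (0.90%) | 15 (0.50%) |
| 2.0% | 60 | 54 (1.80%) | 30 (1.00%) |

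In the middle row, the exact 95% interval is 0.68% to 1.42% with all 30 events counted, 0.59% to 1.31% with 27, and 0.28% to 0.82% with 15. At 50% missed, the interval no longer covers the assumed true 1.0%; at 10% missed it does.

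**The case against.** The strongest reply is that the Note to Table 2 instructs the person grading. Since 8.3.9 sends the investigator back to Table 2, the entered grade should already reflect oxygen and SpO2. That stands: the loss needs a misgraded, unknown or absent entry. Protocol 8.6.5.2 also lets the sponsor query any CRF content, so checks of this kind may exist outside the SAP. A missing grade is shown openly as unknown, and the analysis is exploratory with no decision rule. Death does not depend on the grade, nor does hospitalization or death.

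Three stronger readings are tempting, and the documents do not support them.

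- A reader might infer that SAP 7 reverses the protocol by blanking what should be graded up. SAP 7 does not say that an oxygen-versus-grade mismatch is inconsistent data, nor which field would be blanked, and the handling list is not shown. Cases 2 and 4 under Table 3 keep worsening as present where it is judged to have occurred. Blanking is possible but not stated.
- A reader might infer that recorded oxygen is ignored outside descriptive tables. It also enters the hospitalization sensitivity definition. It does not enter any severity endpoint.
- A reader might infer that the note under Table 3 lists every check. It covers only the comparison that the table makes.

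There is also a fair objection to replacing the physician's grade with a derived one. Among ungraded patients this would recover events but never non-events. At baseline, the 30-day window (SAP Table 2) and the lowest same-day SpO2 rule (SAP 6.3) could raise a start grade on a stale or stray reading and hide later worsening. A derived grade therefore belongs in a sensitivity analysis with baseline grades left as entered.

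**Conclusion.** The point holds as a gap in derivation and checking, not as a conflict between protocol and SAP. The severity endpoints depend wholly on physician-entered fields, and no stated rule compares them with the recorded items that define the grades. Two routes need neither a wrong grade nor any reading of SAP 7: an initially mild patient who worsened with highest severity unknown, and a missing efficacy page. A third, worsening entered as absent despite recorded COVID-19 oxygen, needs a misgraded entry.

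The effect on the moderate II or severe count is downward only. Its size is unknown: the percentages shown rest on assumed event and loss rates, and 3,000 is the safety-set target, not the size of an efficacy set. The remedy uses data already collected and is worth making.

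**What to change.** Keep the physician's grade as the primary analysis. In SAP 6.2, 8.2.4.1 and 10.3:

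- (a) Query any post-start highest severity below the Table 2 grade implied by COVID-19 oxygen, mechanical ventilation or SpO2 recorded during the observation period.
- (b) Report how many patients with such records are discordant or ungraded.
- (c) Add a sensitivity tabulation of worsening and of moderate II or severe that applies the Table 2 higher-grade rule to those patients, leaving baseline grades as entered.
- (d) State that SAP 7 does not blank an entered severity grade solely because of such a conflict.

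The cost is SAP wording, one derivation and some extra queries; no new data are needed. If queries can no longer be raised, (b) to (d) remain possible. The sensitivity analysis may show a slightly higher proportion of severe outcomes, and among ungraded patients it recovers events but not non-events. It is also only a floor, because ICU admission, which Table 2 grades as Severe, is not a listed CRF item.
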